### **9.2.1.3 Treatment phase: Regular study visits from Visit 1 onwards - amended**

Patients will return to the study site for the first on-treatment visit one month following randomization (Visit 1, with a permitted time window of  $\pm$  10 days). Further regular treatment visits (all with a permitted time window of  $\pm$  4 weeks) will be performed 3 months (Visit 2), 6 months (Visit 3), and 12 months (Visit 4) after randomization, and then every 6 months until the study end will be announced (see Table 9-1).

At each on-site visit in the treatment phase, patients will be asked about the occurrence of potential study efficacy outcome events, bleeding events, and AEs/SAEs. If a suspected study efficacy outcome event or bleeding event is reported, the respective eCRF page will be completed and an adjudication package expeditiously compiled and submitted to the ICAC.

The following measures/documentations will be performed at each study visit:

- check for the occurrence of study efficacy outcome events since the last study visit;
- check for the occurrence of bleeding events since the last study visit;

---

 Last sentence added with Protocol Amendment 4 (change no. 12).

- complete all eCRF outcome event, bleeding event and Health Care Resource Utilization (HCRU see Section 9.7.3) pages if applicable
- check for the occurrence of AEs/SAEs since the last study visit (for events exempted from AE/SAE reporting, see Section 9.6.1.3);
- document any changes in concomitant medications since the last study visit;
- assess the patient's PAD Symptom Status;
- If the following laboratory evaluations have been performed since the last study visit and are available in the medical record, it is requested that this information be recorded in the eCRF: HbA1c, creatinine, total cholesterol, HDL cholesterol, LDL cholesterol, ALT(SGPT), AST(SGOT), total bilirubin, hemoglobin, hematocrit, platelet count;
- QoL assessment with EQ-5D (questionnaires should be completed before the other visit procedures);
- Walking Impairment Questionnaire (questionnaires should be completed before the other visit procedures);
- assess vital signs (blood pressure, pulse rate);
- perform ABI (or TBI);
- collect study medication and study ASA bottles dispensed at the previous visit and count and document number of returned tablets. Document any treatment interruptions, if applicable;
- dispense new bottles of study medication and study ASA with patient instructions;
- remind patient to return with the study medication and study ASA dispensed bottles at their next visit.

#### 9.2.1.4 End of treatment (EOT) visit - amended

Once the Sponsor announces the end of the study, all patients must return to their study site within 4 weeks in order to complete the EOT visit. **Study medication and study ASA will be stopped at this visit**, and it will be left to the discretion of the investigator to initiate any antiplatelet or anticoagulation therapy during the transition of care to the patient's personal physicians.

Likewise, an EOT visit should be performed in those patients who leave the study permanently in spite of any attempts to hold the patient on study observation (see Section 6.3.1).

The following measures/documentations will be performed at the final on-site visit:

 Bullet added with Protocol Amendment 4 (change no. 17)

 Bullet added with Protocol Amendment 4 (change no. 12)

 Bullet added with Protocol Amendment 4 (change no. 19)

 Prior to Protocol Amendment 4, this was "perform ABI (or TBI for non-compressible tibial arteries)" (change no. 5).

 Wording revised with Protocol Amendment 4 (change no. 17)

- check for the occurrence of study efficacy and safety outcome events since the last study visit and obtain all supportive information required to complete assessment of these outcome events;
- check for the occurrence of AEs/SAEs since the last study visit (for events exempted from AE/SAE reporting, see Section 9.6.1.3);
- documentation of any changes in concomitant medication since the last study visit;
- assess the patient's PAD Symptom Status;
- QoL assessment with EQ-5D (questionnaires should be completed before the other visit procedures);
- Walking Impairment Questionnaire (questionnaires should be completed before the other visit procedures);
- assess vital signs (blood pressure, pulse rate);
- perform ABI (or TBI);
- collect study medication and study ASA bottles dispensed at the previous visit and count and document number of returned tablets. Document any treatment interruptions, if applicable;
- arrangement of final post-study treatment follow-up phone call.

### **9.2.1.5 Post-study treatment follow-up visit (PS-FU): one month post-EOT (± 1 week)**

Patients will be contacted **by telephone** one month after the EOT visit to allow for collection of final safety data and patient's vital status at study end.

## **9.3 Population characteristics**

### **9.3.1 Demographics**

The following demographic data will be recorded in the eCRF at the screening visit:

- age,
- sex,
- race/ethnicity,
- body weight (kg),
- body height (cm),
- calculated BMI.

---

 Bullet added with Protocol Amendment 4 (change no. 12)

 Bullet moved with Protocol Amendment 4 (change no. 17)

 Prior to Protocol Amendment 4, this was "perform ABI (or TBI for non-compressible tibial arteries)" (change no. 5).

### 9.3.2 Medical history

Medical history findings (i.e., previous diagnoses, diseases or surgeries) meeting all criteria listed below will be collected as available to the investigator at the screening visit:

- not pertaining to the study indication,
- start before signing of the informed consent,
- considered relevant for the patient's study eligibility.

Special attention must be paid to the PAD-related medical history:

- PAD-related and cardiovascular disease history (MI, angina, intermittent claudication, diabetes, renal dysfunction, heart failure, pacemaker, defibrillator, TIA, stroke, hypertension, etc.);
- PAD-related and cardiovascular surgical and endovascular disease history (coronary percutaneous transluminal coronary angioplasty, atherectomy, PCI, coronary artery bypass graft, peripheral artery bypass surgery, peripheral percutaneous transluminal angioplasty, limb or foot amputation, etc.);
- Medical history of bleeding risk and bleeding (liver diseases, gastrointestinal diseases with bleeding, erosions, ulceration, obstruction, perforation; previous bleeding requiring transfusion, etc.).

Instructions on the differentiation between (i) medical history and (ii) adverse events can be found in Section [9.6.1.1](#).

### 9.3.3 Definition of qualifying revascularization procedure - amended

For the purposes of the current study, the qualifying revascularization procedure (surgical or endovascular) must include a technically successful procedure distal to the external iliac artery in the past 10 days, and hemostasis must be assured.

Patients under consideration for this trial may have a treatment plan that focuses on a single procedure or staged procedures where not all revascularizations will necessarily be completed at one time. Preferably, the qualifying revascularization should be the last planned procedure.

**Surgical procedure:** open surgical procedures in the lower extremity for PAD. This can include a variety of procedures, bypass conduit materials, and extra-anatomic operations.

**Endovascular procedure:** catheter-based procedures and hybrid procedures (those procedures involving aspects of both endovascular and surgical revascularizations) for PAD.

The details about the qualifying revascularization procedure will be recorded at the randomization visit in the eCRF.

**Successful procedure:** the qualifying revascularization (regardless of type of procedure) procedure must be deemed technically successful by meeting the following criteria:

- technical success of the procedure with no immediate plan for re-intervention and per the investigator's discretion, the patient can safely be placed on an anticoagulant at the time of randomization;

 Section revised with Protocol Amendment 4 (change no. 4, 6, 7, 14 and 17) and Protocol Amendment 5 (see change no. 4).

- demonstrated graft or vascular patency of the qualifying revascularization procedure prior to randomization. Graft or vascular patency is at the discretion of the investigator and can be demonstrated by a variety of means including imaging, hemodynamic and/or physical findings.

Sites may be required to submit source documents from the qualifying revascularization procedure for central data verification. 

## 9.4 Efficacy

### 9.4.1 Assessments and procedures at occurrence of primary efficacy events - amended

In addition to the interviews performed during the regular on-site visits, all study patients are requested to inform the site as soon as possible if they have been hospitalized (regardless of reason) or have experienced other significant adverse medical events in order to ensure timely identification of potential study efficacy outcome events and bleeding events.

The analysis of study efficacy outcome events will be based on events as adjudicated by the ICAC. Thus, the occurrence of study efficacy outcome events must be reported on Outcome/CV Event reporting forms, as described in the Endpoint Event Site Manual, and will undergo adjudication by the ICAC. All potential coronary ischemic events, cerebrovascular events and peripheral ischemic events should also be reported on the Outcome/CV Event reporting forms.

The following events will be assessed for primary efficacy (for event definition see Section 9.4.2):

- MI,
- Ischemic stroke,
- CV death,
- ALI,
- Major amputation due to a vascular etiology.

Please note that these study efficacy outcome in addition to bleeding events are exempted from AE/SAE reporting (see Section 9.6.1.3.3).

In addition to investigator-identified study efficacy outcome and bleeding events, safety data will be reviewed regularly for potential major vascular thrombotic events. In particular, Medical Dictionary for Regulatory Activities (MedDRA) preferred terms assigned to investigator-reported AEs will be screened for potential study efficacy outcome and bleeding events and investigators may then be asked to further investigate whether or not a study efficacy outcome or bleeding event occurred and potentially initiate the outcomes reporting process.

Study efficacy outcome events will be continuously collected from signing of the ICF to study end (including the post-study treatment follow-up call).

 Sentence added with Protocol Amendment 5 (change no. 6).

 Sentence revised with Protocol Amendment 5 (change no. 7).

 Sentence revised with Protocol Amendment 4 (change no. 23).

#### 9.4.2 Definition of study efficacy outcome events

The following definitions are provided for the purposes of this study:

**Myocardial infarction (MI):** the definition of acute MI is based on the evidence of myocardial necrosis in a clinical setting consistent with acute myocardial ischemia, using the universal MI definition [[Thygesen et al. 2012](#)].

**Ischemic stroke:** the definition of ischemic stroke will be an acute episode of neurological dysfunction caused by focal or global brain vascular injury and includes all strokes that are not of a primary hemorrhagic etiology. This includes fatal and non-fatal strokes.

**Cardiovascular (CV) death:** all deaths will be assumed CV in nature unless a non-CV cause can be clearly shown.

**Acute limb ischemia (ALI):** for the current study, ALI is defined as clinical history and presentation consistent with a sudden significant worsening of limb perfusion requiring hospitalization and

- a new pulse deficit with associated rest pain, pallor, paresthesia, or paralysis and either
  - confirmation of arterial obstruction by imaging, limb hemodynamics, intraoperative findings, or pathological evaluation

OR

- requiring thrombolysis, thrombectomy, or urgent revascularization.

**Major amputation due to a vascular etiology:** for the current study, this is operationally defined as above-the-ankle amputation that is:

- non-traumatic

AND

- due to a vascular etiology which includes worsening perfusion of the limb but excludes foot sepsis as the primary indication for amputation.

Detailed definitions for these efficacy outcomes are provided in a separate ICAC charter.

#### 9.4.3 Efficacy variables

##### 9.4.3.1 Primary efficacy variable

The primary efficacy outcome of the study is a composite endpoint consisting of:

- the time from randomization to the first occurrence of any component of the following major thrombotic vascular events: MI, ischemic stroke, CV death, ALI, and major amputation due to a vascular etiology.

##### 9.4.3.2 Secondary efficacy variables - amended

The secondary efficacy variables of the study are:

- time from randomization to the first occurrence of MI, ischemic stroke, coronary heart disease mortality, ALI, and major amputation of a vascular etiology;

 Paragraphs about ischemic stroke, acute limb ischemia, and major amputation due to a vascular etiology revised with Protocol Amendment 4 (change no. 24).

- time from randomization to the first occurrence of an unplanned index limb revascularization for recurrent limb ischemia (subsequent index leg revascularization that was not planned or considered as part of the initial treatment plan at the time of randomization);
- time from randomization to the first occurrence of hospitalization for a coronary or peripheral cause (either lower limb) of a thrombotic nature;
- time from randomization to the first occurrence of MI, ischemic stroke, all-cause mortality, ALI, and major amputation of a vascular etiology;
- time from randomization to the first occurrence of MI, all-cause stroke, CV death, ALI, and major amputation of a vascular etiology;
- time from randomization to the first occurrence of all-cause mortality.
- time from randomization to the first occurrence of venous thromboembolic (VTE) events;

#### **9.4.3.3 Other efficacy variables - amended**

Other efficacy variables of the study are:

- time from randomization to the first occurrence of all subsequent limb revascularizations of a lower extremity that were not planned or considered as part of the initial treatment plan at the time of randomization;
- time from randomization to the first occurrence of above ankle amputation of the index leg or major re-intervention (e.g., new bypass graft, jump/interposition graft revision, or thrombectomy/thrombolysis);
- time from randomization to the first occurrence of all-cause amputations;
- patient reported outcomes using disease and non-disease specific questionnaires (EQ-5D and WIQ)
- serial changes in limb hemodynamics (ABI/TBI).

### **9.5 Pharmacokinetics / pharmacodynamics**

No pharmacokinetic/pharmacodynamic evaluation will be performed.

### **9.6 Safety**

#### **9.6.1 Adverse events**

Introductory note: Due to the broad knowledge about the safety of rivaroxaban based on the comprehensive clinical and post-marketing safety databases available to date, rules for recording and expedited reporting of AEs/SAEs will follow a targeted approach in order to

 Bullet revised with Protocol Amendment 4 (change no. 8) and Protocol Amendment 5 (change no. 2).

 Bullet revised with Protocol Amendment 4 (change no. 8).

 Bullet added with Protocol Amendment 4 (change no. 13).

 Principles of targeted safety data collection are laid down in the FDA Draft Guidance for Industry "Determining the Extent of Safety Data Collection Needed in Late Stage Premarket and Post approval Clinical Investigations" (February 2012)

facilitate the study documentation. The exemptions from AE/SAE documentation and SAE reporting are described in Section [9.6.1.3.2](#) and Section [9.6.1.3.3](#).

### 9.6.1.1 Definitions

#### Definition of adverse event (AE)

In a clinical study, an AE is any untoward medical occurrence (i.e., any unfavorable and unintended sign [including abnormal laboratory findings], symptom or disease) in a patient or clinical investigation patient after providing written informed consent for participation in the study. Therefore, an AE may or may not be temporally or causally associated with the use of a medicinal (investigational) product.

A surgical procedure that was planned prior to the start of the study by any physician treating the patient should not be recorded as an AE (however, the condition for which the surgery is required may still be considered an AE).

In the following differentiation between medical history and AEs, the term "condition" may include abnormal e.g., physical examination findings, symptoms, diseases, laboratory, ECG.

- Conditions that started before signing of informed consent and for which no symptoms or treatment are present until signing of informed consent are recorded as medical history (e.g., seasonal allergy without acute complaints).
- Conditions that started before signing of informed consent and for which symptoms or treatment are present after signing of informed consent, at unchanged intensity, are recorded as medical history (e.g., allergic pollinosis).
- Conditions that started or deteriorated after signing of informed consent will be documented as adverse events. This includes intercurrent illnesses.

#### Definition of serious adverse event (SAE)

An SAE is classified as any untoward medical occurrence that, at any dose, meets any of the following criteria (a – f):

- a. Results in death.
- b. Is life-threatening.

*The term 'life-threatening' in the definition refers to an event in which the patient was at risk of death at the time of the event, it does not refer to an event which hypothetically might have caused death if it were more severe.*

- c. Requires inpatient hospitalization or prolongation of existing hospitalization.

*A hospitalization or prolongation of hospitalization will not be regarded as an SAE if at least one of the following exceptions is met:*

- the admission results in a hospital stay of less than 12 hours
- the admission is pre-planned (e.g., elective or scheduled surgery arranged prior to the start of the study; admission is part of the study procedures as described in Section [9.2](#))
- the admission is not associated with an AE (e.g., social hospitalization for purposes of respite care).

*However, it should be noted that invasive treatment during any hospitalization may*

*fulfill the criterion of 'medically important' and as such may be reportable as an SAE dependent on clinical judgment. In addition, where local regulatory authorities specifically require a more stringent definition, the local regulation takes precedence.*

- d. Results in persistent or significant disability / incapacity.

*Disability means a substantial disruption of a person's ability to conduct normal life's functions.*

- e. Is a congenital anomaly / birth defect.
- f. Is another serious or important medical event as judged by the investigator.

### **9.6.1.2 Classifications for adverse event assessment**

All AEs requiring documentation will be assessed and documented by the investigator according to the categories detailed below.

#### **9.6.1.2.1 Seriousness**

For each AE, the seriousness must be determined according to the criteria given in Section 9.6.1.1.

#### **9.6.1.2.2 Causal relationship**

The assessment of the causal relationship between an AE and the administration of treatment is a decision to be made by the investigator, who is a qualified physician, based on all information available at the time of the completion of the eCRF.

Causality should be assessed as detailed in the eCRF. If the investigator feels that the event cannot be firmly attributed to one of the study treatments (e.g., owing to a suspected underlying interaction), the same assessment will be documented for each study treatment.

The assessment is based on the question whether there was a "reasonable causal relationship" to the study treatment in question.

Possible answers are "yes" or "no".

An assessment of "no" would include:

1. the existence of a highly likely alternative explanation, e.g., mechanical bleeding at surgical site.  
or
2. non-plausibility, e.g., the patient is struck by an automobile when there is no indication that the drug caused disorientation that may have caused the event; cancer diagnosed a few days after the first drug administration.

An assessment of "yes" indicates that the AE is reasonably associated with the use of the study treatment.

Important factors to be considered in assessing the relationship of the AE to study treatment include:

- the temporal sequence from drug administration: The event should occur after the drug is given. The length of time from drug exposure to event should be evaluated in the clinical context of the event.

- Recovery on drug discontinuation (de-challenge), recurrence on drug re-introduction (re-challenge): Patient's response after de-challenge or re-challenge should be considered in view of the usual clinical course of the event in question.
- Underlying, concomitant, intercurrent diseases: Each event should be evaluated in the context of the natural history and course of the disease being treated and any other disease the patient may have.
- Concomitant medication or treatment: The other drugs the patient is taking or the treatment the patient receives should be examined to determine whether any of them might have caused the event in question.
- Known response pattern for this class of drug: Clinical/preclinical.
- Exposure to physical and/or mental stresses: The exposure to stress might induce adverse changes in the patient and provide a logical and better explanation for the event.
- The pharmacology and pharmacokinetics of the study treatment: The pharmacokinetic properties (absorption, distribution, metabolism and excretion) of the study treatment, coupled with the individual patient's pharmacodynamics should be considered.

#### **9.6.1.2.3 Action taken with study treatment**

Any action on study treatment to resolve the AE is to be documented using the categories listed below. The study treatment action should be recorded as detailed in the eCRF.

- none,
- drug withdrawn,
- drug interrupted,
- not applicable (e.g., study drugs already discontinued),
- unknown.

#### **9.6.1.2.4 Other specific treatment(s) of adverse events**

- none,
- remedial drug therapy,
- other non-drug treatment (e.g., surgery, endovascular interventions).

#### **9.6.1.2.5 Outcome**

The outcome of the AE is to be documented as follows:

- recovered/resolved,
- recovering/resolving,
- recovered/resolved with sequelae,
- not recovered/not resolved,
- fatal,
- unknown.

### **9.6.1.2.6 Intensity - amended**

The intensity of an AE is to be classified according to the following categories:

- mild,
- moderate,
- severe.

### **9.6.1.3 Targeted safety data collection**

Targeted safety data collection is aimed to improve the value of safety data collected by focusing on patient safety and to concentrate the attention on key data to improve clarity of safety reports.

#### **9.6.1.3.1 Assessment of bleeding events**

Bleeding events, which are specific safety outcomes of this study, will be continuously monitored from signing of the ICF until post-study treatment follow-up visit.

All bleeding events will be reported on the designated bleeding reporting forms in the eCRF. Since bleeding events are recorded as safety outcome and the risk profile of rivaroxaban has been established in multiple previous studies, these events are not required to be recorded as an AE/SAE and thus are exempted from SAE reporting.

Bleeding occurring after randomization that is related to the index revascularization procedure (e.g. bleeding requiring an unplanned surgical take-back operation to manage) will also be reported, including details of the management of the bleeding event and any limb complications (e.g., resulting in major amputation or compartment syndrome requiring surgical management). These events will be reviewed by the IDMC on a regular basis and not reported as SAEs.

Potential major bleedings occurring after randomization will undergo adjudication by the ICAC. Major bleeding as adjudicated per TIMI classification is considered the primary safety outcome of the study, but other bleeding types (e.g., based on BARC and ISTH criteria) will also be evaluated as defined in the ICAC charter.

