### **9.6.1.3.3 Reporting of serious adverse events and study-specific exemptions - amended**

The common definition of SAEs is given in Section 9.6.1.1. Each SAE must be followed up until resolution or stabilization by submission of updated reports to the designated recipient.

The efficacy and safety outcomes in this study will be collected in the eCRF and regularly monitored by the IDMC during the entire course of the study in a timely adequate manner. Due to this targeted surveillance, no AE documentation and no expedited SAE reporting will be performed for these events. Consequently, they will neither be un-blinded nor reported to regulatory authorities, IECs, or investigators. The IDMC will periodically review and assess all safety data for imbalances in safety outcomes. It is believed that in this way patient safety can continue to be monitored throughout the duration of the trial, along with study integrity. If unexpected safety issues are identified, specific amendments will be implemented.

The following rules should be followed:

1. **Primary and secondary efficacy outcome events** occurring after randomization will not be recorded on the AE page and not be reported as SAEs to Sponsor's PV

 Cross-references added by Amendment 4 (change no. 17).

 Wording changed by Amendment 4 (change no. 17).

department, but they will be collected on the specific eCRF pages as an efficacy outcome event.

2. **Safety outcome events** (i.e., bleeding events occurring after signing of the ICF) will not be recorded on the AE page and not be reported as SAEs to Sponsor's PV department, but they will be collected on the specific eCRF pages as a safety outcome event.
3. **All other SAEs (including complications of efficacy or safety outcome events)** that fulfill the seriousness criteria provided in Section 9.6.1.1 need to be collected on the eCRF (AE page) and reported as SAEs to the PV department. All SAEs that fulfill SUSAR criteria will be reported to the concerned authorities by expedited means (see Section 9.6.1.4).
4. **Pregnancies** need to be captured and reported to the Sponsor's PV department within 24 hours, even if classified as non-serious (see Section 9.6.2).

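### Protocol 9.6.1.3.1 and 9.6.1.3.3 are not clearly reconciled on whether serious limb complications of index-procedure bleeding are SAEs, so SAE capture may differ between sites

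*Protocol*

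**What the plan says.** Protocol 9.6.1.3.1 first sets a general rule: "All bleeding events will be reported on the designated bleeding reporting forms in the eCRF", and because they are safety outcomes they are exempt from AE and SAE recording. A separate paragraph then deals with "Bleeding occurring after randomization that is related to the index revascularization procedure". The report on such a bleed covers how it was managed and "any limb complications (e.g., resulting in major amputation or compartment syndrome requiring surgical management"). That paragraph closes: "These events will be reviewed by the IDMC on a regular basis and not reported as SAEs".

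Protocol 9.6.1.3.3 lists the reporting rules. Rule 1 exempts primary and secondary efficacy outcome events after randomization. Rule 2 exempts the safety outcome itself: "bleeding events occurring after signing of the ICF) will not be recorded on the AE page and not be reported as SAEs". Rule 3 keeps everything else in: "All other SAEs (including complications of efficacy or safety outcome events") that meet the seriousness criteria of 9.6.1.1 "need to be collected on the eCRF (AE page) and reported as SAEs to the PV department".

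**The concern.** A compartment syndrome needing surgery after an index-procedure bleed is named in 9.6.1.3.1 as part of the bleeding report, and the next sentence removes the reported events from SAE reporting. In 9.6.1.3.3 the same event is a complication of a safety outcome and, if serious, an SAE. Neither section refers to the other on this point.

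The routing matters. A non-exempt SAE must be notified within 24 hours (9.6.1.3.3). It gets a separate sponsor assessment of seriousness, expectedness and causality (9.6.1.3.2) and is expedited if it meets the SUSAR criteria (9.6.1.4). It also enters the by-arm adverse event tables of SAP 6.4.1. A complication left as a detail on a bleeding form gets none of these. Protocol 3.4 names bleeding as the main risk of the drug and gives the IDMC a particular focus on peri-procedural bleeding, so the reporting rule for its serious consequences should be clear.

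**Working it through.** The documents give no figure on this point and no arithmetic applies. The check sets the rules side by side, using the current protocol text rather than the amendment log.

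**Step 1: two readings of the exemption.** On the narrow reading, the exempted events are the bleeds, and limb complications are details entered on the form. On the broad reading, they are the bleeds together with the limb complications named in the preceding sentence.

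**Step 2: apply each rule to each type of event.**

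| Event | 9.6.1.3.1, narrow | 9.6.1.3.1, broad | 9.6.1.3.3 |
|---|---|---|---|
| The index-procedure bleed | exempt | exempt | exempt (rule 2) |
| Major amputation meeting the 9.4.2 definition | not addressed | exempt | exempt (rule 1, primary efficacy outcome) |
| Compartment syndrome requiring surgery | not addressed | exempt | SAE if serious (rule 3) |
| Amputation outside the 9.4.2 definition | not addressed | exempt | SAE if serious (rule 3) |

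The sections conflict only in the last two rows, and only on the broad reading. A surgically managed limb complication would usually meet the hospitalization criterion in 9.6.1.1, so rule 3 would normally apply. Amputations that fail the vascular-etiology definition stay in the last row because rule 1 covers primary and secondary outcomes only; all-cause amputation is an other efficacy variable (9.4.3.3).

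**Step 3: is the broad reading realistic?** The general paragraph of 9.6.1.3.1 already exempts every bleeding event, and rule 2 does so again. On the narrow reading, the exemption in the index-procedure paragraph adds nothing; only the mention of regular IDMC review is new. What the paragraph adds in substance is management detail and limb complications, so a site could reasonably take those as the object of the exemption.

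**Step 4: where are sites sent?** The introductory note to 9.6.1 and the text of 9.6.1.3.2 point to 9.6.1.3.2 and 9.6.1.3.3. The visit instructions (9.2.1.1 to 9.2.1.4) and footnote f of Table 9-1 point to 9.6.1.3 as a whole, which includes 9.6.1.3.1. A site working from the visit schedule therefore meets both statements.

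**Step 5: would another planned analysis show these events?** SAP 6.4.5 covers TIMI, ISTH and BARC bleeding and bleeding that leads to drug discontinuation. SAP 6.2.8 defines MALE as ALI plus vascular major amputation. SAP 6.2.3 includes all-cause amputation as an exploratory variable, so amputations keep a by-arm display. Compartment syndrome has none in the SAP outside the tables of 6.4.1. Table specifications are in a separate document, so this statement is limited to the SAP.

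**The case against.** The strongest reply is that the sections agree when read naturally. The subject of the 9.6.1.3.1 paragraph is bleeding; limb complications appear only as content of the report. One paragraph earlier, the same pronoun phrase can only mean bleeding events. On that reading a site enters the compartment syndrome on the bleeding form and also reports it as an SAE under rule 3. In addition, the introductory note to 9.6.1 names 9.6.1.3.2 and 9.6.1.3.3, not 9.6.1.3.1, as the source of exemptions. Section 9.6.1.3.2 sends SAE handling to 9.6.1.3.3, and investigators are to be trained on SAE reporting.

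Much of this stands. The text is ambiguous rather than unavoidably contradictory, and the protocol's structure favours rule 3. It does not close the matter, because 9.6.1.3.1 states an exemption of its own in the one paragraph that names limb complications, and the visit instructions do not restrict sites to 9.6.1.3.3.

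It is also true that leaving bleeds out of the SAE tables is the declared targeted-collection design (9.6.1 and 9.6.1.3). That is not in dispute; the point concerns their complications, which rule 3 deliberately keeps in.

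**Conclusion.** The point holds as an unreconciled ambiguity: 9.6.1.3.1 can be read as exempting serious limb complications that rule 3 of 9.6.1.3.3 makes reportable. It is limited to complications that are not efficacy outcomes. The complications remain on the bleeding forms and under regular IDMC review, potential major bleeds are adjudicated, and the primary safety analysis of TIMI major bleeding does not change. The exposure is in pharmacovigilance and SUSAR routing and in the completeness of the SAE tables.

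A reader might infer three stronger things that the documents do not support:

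- *That a site cannot comply with both sections.* It can, on the narrow reading.
- *That these harms do enter the SAE data at some sites only.* No divergent site practice on this point is described. The only stated difference in SAE collection is Japan (SAP 6.4.1), which concerns outcome events and is handled by separate tables.
- *That a number of lost events, or an excess in one arm, can be given.* A count would need the rate of post-randomization index-procedure bleeding, the proportion with a serious non-endpoint limb complication, and the share of sites taking the broad reading. None is given, so no range has a basis.

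The conclusion rests on one assumption: that some sites could take the broad reading.

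**What to change.** Limit the last sentence of the index-procedure paragraph in Protocol 9.6.1.3.1 to the bleeding event itself, and add a cross-reference along these lines: *Limb complications of such bleeding that meet the seriousness criteria and are not themselves primary or secondary efficacy outcomes are recorded on the AE page and reported as SAEs under 9.6.1.3.3, rule 3.*

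Then check index-procedure bleeding forms already completed for serious limb complications without a matching SAE, and query those sites.

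The cost is a short text change and a check of the relevant forms. The downside is a few more SAE reports. No analysis in the SAP needs to change.
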